Parents will be screened to be sure they qualify to participate in the study (See attached Screening Form). Parent(s) will read, have the opportunity to ask questions about, and sign the informed consent form and the HIPPA Authorization Form. Each parent who agrees to participate will complete a Participant Information Form with information about their own height, weight, age, race/ethnicity, primary language, and family history. They will also provide the phone number to their mobile device on the data collection sheet, their child's date of birth, and indicate if they will be answering the surveys since only one parent will be permitted to answer the surveys. To participate, at least one parent must agree to answer the surveys. Then, the participants will be randomized to one of the following groups: feeding text messaging or usual care with safety text messaging. A computer-generated blocked randomization schedule with balanced distribution with regards to sex will be used to place

infants into groups. This stratified allocation will be concealed in opaque, sequentially-numbered sealed envelopes, and opened by study staff. While parents recruited may vary in weight status, income, and race/ethnicity, in a pediatric primary care setting randomizing participants into groups based on these multiple criteria, which are not gathered on parents of patients would be burdensome for clinic staff. Thus, parent participants will be randomized into each study group (usual care or text-messaging) based only on sex of the infant.

After research staff know the group assignment, they will enroll parents into the study using the child’s date of birth and the parents’ mobile phone numbers. See the figure below for the sequence of enrollment events.

[figure not shown]

Figure 1: Flow and Sequence of Enrollment Events

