Texas Health Steps is the recommended schedule for well visits with a pediatric healthcare provider for patients enrolled in Texas Medicaid. The following visits are recommended: 3-5 days, 2 weeks, 2 months, 4 months, 6 months, 9 months, 12 months, 15 months, 18 months, and 2 years. Insurance companies allow well visits at the same interval. Not all parents are able to bring children according to this precise schedule; thus, slightly flexible age ranges will be used for each data collection. The project proposes to gather data from both groups of parents only between 3-30 days, 2-4 months, 6-9 months, and 12 months so that parents who miss attending one of the scheduled visits can be caught at the next one. To track feeding practices, at the 0-30 day, 2-4 month, 6-9 month, and 12 month visits, parents will be given a link to answer questions in a mobile survey in PsychData adapted from the National Health and Nutrition Examination Survey Diet Behavior Nutrition Questionnaire⁵⁷ with additional questions on responsive feeding practices from the Infant Feeding Style Questionnaire (IFSQ)⁵⁸⁻⁵⁹. This link will also be sent by text if the survey is not filled out at the scheduled visit. To track actual intake, one of the research staff will call parents of infants between 2-4 months, 6-9 months, and at 12 months to conduct a 24-hour recall of the infant’s intake. The Healthy-Txt messaging system captures only the data specified by the research protocol. For this study, Healthy-Txt will gather data on whether participants opt out of participation, responses to yes or no questions in the text messages, and whether participants access landing page information. This data is linked to the participants’ (parent’s) mobile phone number. Finally, a chart review of each participating infant’s chart (part of the participating parent/infant dyad) will be conducted by one of the research staff employed at the UNTHSC pediatric clinic. The research staff will keep a master list of the infant’s medical record number (MRN) and a randomly assigned participant ID number. They will use this master list to collect the following data from the infant’s chart: age, weight, and height at 0-30 days, 2-4 month visit, 6-9 month visit, 12 month visit.

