The information on the infant's age, weight, and height gathered from the electronic medical record (EMR) will be stored in a spreadsheet together with the randomly assigned participant ID number. No identifying information will be stored together with the MRN on the master list. The master list will be stored on a secure drive in the UNTHSC department of pediatrics. Only the PI, and the research coordinator will have access to the master list. The de-identified spreadsheet with the infant age, height, and weight data will be shared with the TWU collaborators and research staff for analysis. Information from the 24-hour recall will be recorded on a data collection form with only the randomly assigned participant ID number and when analyzed will be stored in a spreadsheet with only the randomly assigned participant ID number. The co-investigators, together with [name], will be responsible for analyzing the data with assistance from statisticians in the Center for Research Design and Analysis at Texas Woman's University.

Descriptive statistics will be used to describe mean, median, standard deviation, and range for all continuous variables in each group. Frequency and percentage will be calculated to demonstrate categorical variables in each group. Then, independent t tests will be conducted to compare continuous demographic variables between the two groups, and cross-tabulation using chi-square test will be used to compare categorical demographics between the two groups. The relationships between demographic variables and baseline outcomes will also be examined to identify whether any demographic variables need to be controlled for in the primary analyses. In addition, feeding practices will be compared between the two groups using repeated measures analysis of variance (ANOVA) or repeated measures analysis of covariance (ANCOVA). All data will be analyzed using IBM SPSS, version 25, and a $P < 0.05$ is considered significant. The number of participants in part two was determined using a moderate effect size ($f = 0.25$) with 0.8 power to detect a difference between the two groups. With repeated measures ANOVA (2 groups x 3 time points), a total of 37 participants including a 30% drop out rate were required for adequate power.

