- 3) *Data Storage and Confidentiality* – Research data, in hard copy or electronic form (CD, flash memory drive), will be stored and managed in a secure manner according to NIH guidelines as well as state and institutional policies and practices. Further, research documents, including electronic documents containing subject data, identifiers, and linked data, will be securely stored on a password-protected computer and in locked containers (file cabinets, lockers, drawers, etc.) in accordance with standard document management practices. At all times, only listed key personnel specifically designated and authorized by the Principal Investigator shall have access to any research-related documents. All such personnel will be properly trained and supervised regarding the management and handling of confidential materials. The Principal Investigator will assume full responsibility for such training, supervision and conduct.

Surveys on PsychData are encrypted using 256-bit SSL Technology. This encrypts both the questions displayed and the participants' responses. All responses are automatically encrypted. Though highly unlikely, if interception of encrypted data occurs, the data cannot be encoded without the unique encryption key only held by PsychData. Data will be stored on PsychData secure server. It is then held in an isolated database that is only accessible by a researcher with the correct username and password. The researcher has control over all data recorded.

Data gathered by Healthy-Txt on whether participants opt out of participation, responses to yes or no questions in the text messages, and whether participants access landing page information will be linked to the participants' mobile phone number. All Healthy-Txt data is stored on a secure server compliant with HIPAA guidelines.

- 4) *Setting* - The survey will be completed during in-office visits. Parents will be able to complete on-line, mobile surveys before, during, or after their appointment. This link will also be sent by text if the survey

is not filled out at the scheduled visit. Phone calls to patients’ parents will also be made to collect 24-hour recalls of diet. Weight and length of infants will be collected using chart reviews of the infants whose parents participate in the study. Parents will receive text messages in their own locations using their own mobile devices.

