5) Describe plans for *recruitment of subjects*. Parents will be recruited during the first few in-office visits with their infant's healthcare provider. One of the students or the Research Coordinator will visit with interested parents, explain the consent form, answer questions about the study, and get consent. Those participants who decide to participate will be randomized into the control or intervention group at that time. They will fill out a basic information form including their cell phone numbers so that they may begin receiving text messages.

G. Risk/Benefit Assessment

1) This is a minimal risk project that involves providing basic information about feeding to parents of infants either through handout (control group) or text message (intervention group) and basic information about infant safety through text message (control group) or handout (intervention group). There is no direct benefit of participation to subjects other than a possible gain in knowledge and awareness about early nutrition, infant feeding practices (intervention), and infant health and safety guidelines (control).

2) Because the study is expected to provide useful information to parents of infants in a format that is convenient and acceptable to them, the minimal risk is considered acceptable.

3) This method of conducting research is at least as favorable as that provided by providing handouts because it is convenient. In preliminary research involving focus groups, all parents participating reported being willing to receive text messages with feeding advice.

4) Describe any potential RISKS OR DISCOMFORTS in detail.

There is a potential financial risk because carrier message and data rates may apply. Participants will be advised of this risk but will also be receiving incentives to help compensate for any potential financial risk.

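### The first feeding survey, the only possible source of baseline feeding outcomes, can be completed after randomisation and after arm-specific texts have begun

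*Protocol*

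**What the plan says.** **Before allocation.** Section E.1 describes screening and consent, then the form: "Each parent who agrees to participate will complete a Participant Information Form". The form covers the parent's own characteristics, the phone number and the child's date of birth. The next step is "Then, the participants will be randomized to one of the following groups: feeding text messaging or usual care with safety text messaging". The feeding survey is not among the steps listed before it.

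**Timing of allocation.** Section F.5 says of parents who consent: "Those participants who decide to participate will be randomized into the control or intervention group at that time". Phone numbers are collected there so that texts can start. Nothing makes the start of texts conditional on a completed survey.

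**The feeding survey.** Section E.1 gives parents a survey link "at the 0-30 day, 2-4 month, 6-9 month, and 12 month visits". Section E.4 first says "The survey will be completed during in-office visits", then relaxes this: "Parents will be able to complete on-line, mobile surveys before, during, or after their appointment". Sections E.1 and E.4 both add "This link will also be sent by text if the survey is not filled out at the scheduled visit". Section E.1 also provides one reminder text for missed surveys, without excepting the first. Its wording takes for granted that the parent is already receiving messages. The time-burden paragraph in Section G.4 likewise allows completion after the visit.

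**Use in the analysis.** Section E.2 states: "The relationships between demographic variables and baseline outcomes will also be examined". The purpose is to decide which demographic variables to control for in the primary analyses. Feeding practices are then compared by repeated measures ANOVA or ANCOVA.

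**The concern.** A baseline measurement should be fixed before the participant can be affected by allocation. Here the parent may answer the first feeding survey after learning from the texts whether they concern feeding or safety, and after some days or weeks of those texts. Breastfeeding is a target practice, and messages supporting it go to the feeding arm in the first weeks of life, so an early effect is part of what the trial hopes to see.

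Two things could follow. The first survey could already contain part of the treatment effect, so that an analysis using it as the starting point would subtract that part. Or parents could report differently, or fail to respond, depending on their arm. The second effect has no predictable direction.

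**Working it through.** **Step 1. Sequence in the visible text.**

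| Step | Source | Tied to the first survey? |
|---|---|---|
| Screening, consent, information form | E.1 | Survey not listed |
| Randomisation, sealed envelope opened | E.1, F.5 | Not conditional on the survey |
| Text enrolment, messages begin | E.1, F.5 | Not conditional on the survey |
| 0-30 day survey | E.1, E.4 | At the visit, or later by link or reminder; no cut-off |

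No section requires the survey before the envelope is opened or before the first text.

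**Step 2. Possible exposure before a late first survey.** Take enrolment at day 3 and completion at day 30, the ends of the stated window: 30 - 3 = 27 days, and 27/7 = 3.86 weeks. Section E.1 gives a ceiling of two to four texts per week: 2 x 3.86 = 7.7 and 4 x 3.86 = 15.4, or about 8 to 15 messages. E.1 also speaks of up to four in the first four weeks. If that is a total, the figure is about 4 at most. A parent enrolled near day 30 would have far less exposure within the window.

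**Step 3. The plan's own figure.** E.2 gives f = 0.25, power 0.80, alpha 0.05, 2 groups x 3 time points, and 37 participants including 30% dropout. For the group-by-time interaction with k = 2 groups, m = 3 times and sphericity, lambda = f² N m / (1 - rho), with df1 = (k - 1)(m - 1) and df2 = (N - k)(m - 1). The protocol gives no rho; I assume 0.5.

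- N = 28: lambda = 0.0625 x 28 x 3 / 0.5 = 10.5, df = 2 and 52, power 0.812.
- 28 x 1.30 = 36.4, rounded up to 37, which matches.
- With rho = 0.3 or 0.7 the same route gives 50 or 24.
- The between-group main effect at rho = 0.5 would need 86 before dropout, which does not match.

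The sample size therefore appears to rest on the interaction. It does not show which three time points are meant.

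**Step 4. Consequence under each reading.**

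*(a) The first survey is one of the three points.* Let it carry a fraction c of the effect, with the two later points carrying all of it. The group differences follow the pattern (c, 1, 1). Their sum of squares about the mean is (2/3)(1 - c)², so effective f = 0.25 (1 - c).

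*(b) The first survey is an ANCOVA covariate.* With slope 0.5, the adjusted group difference keeps 1 - 0.5c of the effect.

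| c (assumed) | f in (a) | Power in (a), N = 28 | Effect kept in (b) |
|---|---|---|---|
| 0 | 0.250 | 0.81 | 100% |
| 0.10 | 0.225 | 0.72 | 95% |
| 0.25 | 0.188 | 0.55 | 87.5% |
| 0.50 | 0.125 | 0.27 | 75% |

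This table shows direction and sensitivity only. The protocol gives no value for c, which depends on how many parents answer late and how fast the texts act.

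*(c) The three points are 2-4, 6-9 and 12 months, and the first survey is not a covariate.* The first survey is outside the model, so its timing does not bias the comparison. It can still influence which demographic variables are selected. Those variables are collected before randomisation, so adjusting for them does not itself remove treatment effect. The description of feeding at baseline by arm would still mix chance imbalance with early effect.

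**The case against.** **Figure 1 may settle the order.** Section E.1 refers to it for the enrolment sequence, and it is not shown in the text at hand. It could place the survey before randomisation, so a reader should not infer that every first survey is taken after allocation. What stands is narrower: whatever the figure shows, the texted link and the reminder let a first survey be completed late.

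**In-office completion is the stated norm.** E.4 says so, and the link is a fallback. That is right, and it limits how many surveys would be late. It does not set a limit for those that are.

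**Baseline outcomes is not defined.** Weight-for-length z score is also an outcome, and its 0-30 day measurements come from the chart, whatever the survey timing. This is correct, and the point is confined to feeding outcomes. For those, the 0-30 day survey is the only candidate, because the diet recalls start at 2-4 months.

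**The analysis may not use the first survey.** A reader might infer that the primary comparison is biased. The protocol does not support that as a certainty. It states no change-from-baseline analysis and no adjustment for the first survey, and E.2 uses baseline outcomes only to choose demographic covariates. There are four survey occasions but three modelled time points, and the Aim names exactly three later ones, which favours reading (c). E.2 does not name the points, so reading (a) remains open.

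**A size in standard deviations.** A reader might turn f = 0.25 into a planned difference of 0.5 SD and express the bias as a share of it. That conversion belongs to a two-group mean difference, whereas 37 reproduces as an interaction calculation. The late share and the early effect would also have to be invented.

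**Both arms receive texts and feeding handouts.** This is true, so only the content of the texts, and knowing which kind one receives, can separate the arms at the first survey.

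**Conclusion.** The point holds as a permissive rule that should be closed before enrolment. The visible text allows the only feeding survey that can serve as baseline to be answered after allocation and after arm-specific texts have started, with no cut-off.

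The consequence is conditional. If the survey is a modelled time point or an ANCOVA covariate, and the early effect runs in the same direction as the later one, the estimated effect is biased toward no effect. If the model uses only 2-4, 6-9 and 12 months without adjusting for the first survey, the harm is limited to covariate selection and baseline description. Arm-dependent reporting or non-response could act in either direction. No magnitude can be derived from the protocol.

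**What to change.** In Sections E.1, E.4 and F.5:

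- Require the 0-30 day PsychData survey to be completed after consent, and before the envelope is opened and the phone is registered with Healthy-Txt.
- Restrict completion after the appointment, the texted link and the reminder to the 2-4, 6-9 and 12 month surveys.
- Record the date and time of completion of the first survey.
- State that a survey completed after allocation is not treated as baseline.
- Make Figure 1 agree with this order.

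The change reorders steps within one visit and needs no new instrument or extra participants. It costs survey time in clinic. Closing the late route may also leave a few baselines missing or delay some enrolments slightly, which is noticeable in a pilot of 30 to 40 dyads. The order cannot be repaired once parents have been randomised.

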Our long-term *goal* is to identify best practices to prevent early pediatric obesity. The overall **objective** of this proposal is to test the efficacy of a text-messaging program to provide parental feeding advice on feeding practices and weight-for-length z scores. Our central *hypothesis* is that targeted, text messages will be an effective tool to promote healthy feeding practices among parents. Our program will be based on the Health Belief Model²⁴. In particular, the text messages will be constructed to promote motivation for behavior change by influencing perceived susceptibility to the risk of early obesity, demonstrating to parents the benefits of long breastfeeding duration and healthy feeding practices, reducing perceived barriers to adopt healthy feeding practices, providing cues to adopt healthy feeding behaviors, and providing practical tips for adopting behaviors to improve self-efficacy related to healthy feeding practices.

Aim: Compare the impact of targeted text messages versus usual care on feeding practices of parents of infants at 2-4, 6-9 months, and 12 months and on infant weight-for-length z scores at 6-9 and 12

months. Hypothesis: Text messages will be more effective at generating obesity-preventive feeding practices and normal weight-for-length z scores compared to usual care.

B. Background and Significance –

Childhood obesity poses a great risk to the health of US children and adults because it is associated with increased risk for health problems including hyperlipidemia, diabetes, hypertension, and fatty liver disease.²⁵⁻³⁵ Rapid weight gain in infancy is associated with obesity in both children and adults.^{20, 36-41} Factors known to be related to early rapid weight gain and obesity include parental obesity, birth weight, early cessation of breastfeeding, and early introduction of solids.^{1-2, 4-23} Since birth weight is non-modifiable, encouraging adoption of hypothesized obesity-protective parental feeding practices such as breastfeeding, avoiding SSBs, appropriate introduction of first foods, and responsive feeding is essential.¹⁵⁻²² Motivating parents to modify these early childhood feeding practices will promote achievement of one of the Healthy People 2020 objectives: to reduce obesity in children ages 2 to 5.³

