D. Investigator Experience - [name] is an experienced pediatrician and Associate Professor in the Department of Pediatrics at the University of North Texas Health Science Center (UNTHSC) with ample research interest and background in investigating obesity and type 2 diabetes in children. She has conducted several clinical trials and research studies involving children, has published in peer reviewed journals. Thus, she is experienced with conducting research in a clinical setting. She will be collaborating with [name], Chair and Professor of Pediatrics, UNTHSC and two researchers from Texas Woman's University (TWU)—Drs. [name] and [name]. [name] has about 40 years of clinical and research experience and has published about 100 articles in peer reviewed journals. [name] has a long background as a pediatric dietitian and has worked with parents of infants providing counseling and advice for over 17 years. She also has past experience conducting survey-based research. [name] is a Certified Health Education Specialist and a Certified Health and Wellness Coach who has over 28 years of experience in health education and health promotion, including presentations and publications on child and adolescent health. [name] also has experience conducting both quantitative and qualitative research. Drs. [name] and [name] will be working with experts in research methods from the Center for Research Design and Analysis at TWU.

E. Experimental Design and Methods -

1) *Methods and Procedures* - Thirty to 40 parent/infant dyads/triads of infants aged 3-30 days (15 to 20 parent/infant dyads in each group) will be recruited from the UNTHSC Pediatric Clinic.

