Both groups of participants will receive an initial text message. Then, they will receive minimally-customized, motivational text messages⁵⁴ up to two to four times per week⁵⁵ during their first 12 months of life. These messages will be free of charge except for any potential carrier message and data rates. During the infant’s first weeks of life, frequency may be higher (up to four times in the infant’s first four weeks of life) and then decrease to once per week as the infant gets older. Intervention participants will receive text messages with feeding advice and handouts provided to all clinic patients with feeding and general infant safety advice. Control, usual care participants will receive handouts with feeding and general infant health and safety advice and text messages with general infant health and safety advice. The schedule for sending texts is noted in the attached Excel files containing feeding and safety information. The schedule for distributing handouts with both feeding advice and general infant health and safety advice is noted below, and the handouts are included as attachments.

Intervention and Control Participants

Days/Months	Handout-Feeding and Safety Advice
3-30 days (2-5 days and 1 month visits)	A.Inf.PH.2-5day A.Inf.PH.1month
2-4 months (2 and 4 month visits)	A.Inf.PH.2month A.Inf.PH.4month
6-9 months (6 and 9 month visits)	A.Inf.PH.6month A.Inf.PH.9month
12 months	A.Inf.PH.12month

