Parents will have the opportunity to opt out of the messages by replying “STOP” at any time. Opting out will be viewed as non-participation. Short (less than 160 character) text messages will be provided at scheduled intervals. Parents who indicate their infant will be breastfeeding will receive messages aimed at supporting breastfeeding. Parents who indicate their infant is receiving formula will receive messages aimed at supporting appropriate formula feeding. When babies/parents are ready to start solids, the parents will text “solids” to 41411 to begin receiving messages pertaining to feeding their baby solids. Messages will offer motivational, gain- or loss- framed, feeding-related messages, which will not convey information regarding past, present or future medical conditions or care. Some messages will contain links to a parent landing page (Web page), where parents may read content with more information on feeding advice. The landing pages will also contain links to appropriate external web pages with additional information or videos related to feeding and infant nutrition care. The text messages will be delivered using a service called Healthy-Txt, which is in use in other pediatric primary care settings (such as UCLA) to provide appointment reminders and other messaging.⁵⁶ TWU nutrition and health studies professors, UNT-HSC pediatricians, nutrition graduate students, and a TWU communications professor specializing in feeding assisted with development of the text-messaging content and Web landing page materials. Participants will not be able to respond to texts. Participants will receive a text with the first text in each group to “Remember to call 911 in a medical emergency”.

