Texas Woman’s University’s IRB will rely on the North Texas Regional IRB and will sign an Institutional Authorization Agreement upon approval of the study by the North Texas Regional IRB . ([name], IRB Coordinator, [contact]; [contact])

5) *Laboratory methods and facilities* - N/A

6) *Estimated Period of Time to Complete the Study* –

Task	Year 1 (September 30, 2018-August 31, 2019) Quarters (3-months)				Year 2 September 30, 2019- February 28, 2020 Quarters (3-months)	
	9/30-11/30	12/1-2/28	3/1-5/31	6/1-8/31	9/1-11/30	12/1-2/28
Participant Recruitment	X					
Data Collection	X	X	X	X	X	
Data Analysis		X	X	X	X	
Manuscript Preparation						X

F. Human Subjects - Describe the characteristics of the research population:

1) *Sample Size*: 30-40 parent/infant dyads. Both parents may participate and receive separate text messages, but one compensation item will be provided per family.

2) Describe both *Inclusion / Exclusion Criteria*.

Inclusion criteria will be:

- Parents with age 18 and older. We don’t include parents younger than 18 because it is suspected that their concerns regarding feeding and sources of feeding advice may be different compared to adult parents.
- Healthy and term infants (born at 37 weeks or later) establishing care with the healthcare provider between 3-30 days of life and their infants (Parent/infant dyads).

- Parents must be able to speak and read English well. All researchers speak only English, thus we would like to pilot this in an English-speaking population first to make sure the messages are well crafted.
- Parents must have a mobile phone that can receive text messages and access the Internet.

Exclusion criteria will include:

- Infants with congenital anomalies, genetic disorders, or who develop failure-to-thrive during the intervention

3) Describe intended *gender, age range, intended racial and ethnic distribution*.

Both fathers and mothers are sought for participation. However, only one parent may fill out the questionnaires and will receive incentives for their participation. Participants must be adult parents of infants, but there is no upper age limit for participation. Because of the make-up of the clinic population, it is thought that about half of participants will be Hispanic to reflect the clinic population.

4) Identify the *source(s) from which you will obtain your study population*. All participants will be parents of infants and their infants attending the UNT-HSC Pediatric Clinic.

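### The exclusion for failure-to-thrive arising during the intervention can only remove infants after randomisation, on an event closely tied to the weight-for-length outcome

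*Protocol*

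**What the plan says.** - **Exclusion (F.2).** The exclusion list reads "Infants with congenital anomalies, genetic disorders, or who develop failure-to-thrive during the intervention".
- **Timing (F.5, with E.1 and F.2).** Infants enter at 3 to 30 days of life. Once parents agree, "Those participants who decide to participate will be randomized into the control or intervention group at that time". Messages then run through the first 12 months of life.
- **Outcome (A, Aim).** The arms are compared on feeding practices and on infant weight-for-length z scores at 6-9 and 12 months. The hypothesis is that the texts do better at producing normal z scores.
- **Source of growth data (E.4).** "Weight and length of infants will be collected using chart reviews of the infants whose parents participate in the study".
- **Opting out (E.1).** "Parents will have the opportunity to opt out of the messages by replying “STOP” at any time", and then: "Opting out will be viewed as non-participation".
- **Risks (G).** Financial, informational, emotional and time risks are described. Poor growth is not among them. Failure-to-thrive appears only as a reason for exclusion.

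**The concern.** An eligibility criterion should rest on facts known before allocation. Failure-to-thrive that develops during the intervention is not known then, so this clause works as a removal rule after randomisation. The event is one of poor growth, and growth is what the z score measures.

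The intervention is meant to change how infants are fed in order to prevent obesity, so growth that is too slow is the obvious adverse direction. A rule that sets those infants aside acts most strongly when the intervention has an effect on growth. Two things are at stake: the comparison of randomised groups on the z score, and the trial's ability to see this harm at all.

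The opt-out sentence raises a lesser question. The arms receive different texts (feeding or safety), so reasons for replying STOP may differ by arm. If such dyads left the data, that too would be a selection after randomisation.

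**Working it through.** The protocol gives no figure on this point to reproduce, and its sample size calculation does not enter.

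**Step 1: order of events.** Randomisation takes place at consent, at age 3-30 days (E.1, F.2, F.5). The clause concerns an event during the intervention, which starts afterwards. Every infant it catches has therefore already been randomised.

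**Step 2: one infant removed.** Inputs: 15 to 20 dyads per arm (E.1). Assumed: the removed infant has z = -2.5 and the others in that arm average 0.

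- Arm mean with the infant kept: -2.5/n. With the infant removed: 0. Shift = 2.5/n.
- n = 20: 2.5/20 = 0.125. n = 15: 2.5/15 = 0.167.
- If instead the whole arm, this infant included, averages 0, the shift is 2.5/(n - 1): 2.5/19 = 0.132 or 2.5/14 = 0.179.

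The full shift enters the group difference only if the other arm loses nobody.

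**Step 3: a downward shift of the whole arm.** Assumed: z is normal with SD 1, the control mean is 0, the intervention mean is m, and infants below a cut-off c are removed in both arms. The mean of those kept is m + φ(c - m)/[1 - Φ(c - m)].

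Example with c = -2 and m = -0.50:
- Control: 0 + 0.0540/0.9772 = 0.055.
- Intervention: -0.50 + 0.1295/0.9332 = -0.361.
- Observed difference: -0.361 - 0.055 = -0.416, against a true -0.50.

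| Cut-off c | True difference | Observed | Attenuation | Removed, control / intervention |
|---|---|---|---|---|
| -2 | -0.25 | -0.215 | 13.9% | 2.3% / 4.0% |
| -2 | -0.50 | -0.416 | 16.7% | 2.3% / 6.7% |
| -2 | -0.80 | -0.636 | 20.5% | 2.3% / 11.5% |
| -1.645 | -0.25 | -0.194 | 22.2% | 5.0% / 8.2% |
| -1.645 | -0.50 | -0.372 | 25.7% | 5.0% / 12.6% |
| -1.645 | -0.80 | -0.560 | 30.0% | 5.0% / 19.9% |
| either | 0 | 0 | none | equal |

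(Attenuation is computed from unrounded values.)

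**Step 4: harm confined to the tail.** Suppose 2 of 20 intervention infants are at z = -3, the other 18 average 0, and the control arm averages 0. The true difference is (2 × -3)/20 = -0.30. After removal it is 0.

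**Step 5: proportion with a normal z score.** If 18 of 20 infants are normal (90%) and one of the other two is removed, the figure becomes 18/19 = 94.7%. On mean z the rule hides a fall; on the proportion normal it flatters the arm that loses infants.

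**Step 6: the opt-out sentence.** E.1 equates STOP with non-participation, and E.4 ties chart review to infants whose parents participate. Read together, these suggest removal. Against that, E.1 records opt-out as a data item, F.1 lets both parents receive separate texts, and no section says that data are dropped or that chart review ends.

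**The case against.** **The trial is a small pilot in healthy term infants, and failure-to-thrive may not occur.** This stands as to frequency: no rate is given. But with 15 to 20 per arm a single case is enough to move a mean, and the rule is wrong whether or not it is ever used.

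**The clause may be meant to govern stopping the intervention, and the analysis set belongs in a statistical analysis plan.** A plan not seen here may well define the analysis set. The clause, however, is a stated exclusion in the protocol, not a silence left for that plan to fill. Whether messages or other care change for such infants is a clinical matter and is not addressed here; it can be kept apart from whether their data are analysed.

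**Failure-to-thrive is undefined, so it need not mean low weight-for-length.** This is correct and limits the wording. The event is closely related to the outcome, but the protocol does not show that it is the same measurement.

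**A reader might infer that STOP is a second rule removing randomised dyads.** The text does not go that far. It does not say what happens to data already collected or to later chart review, and the consent form, which bears on this, is a separate document. Nor is all data collection independent of texting: the back-up survey link and the single reminder go by text (E.1, E.4). The sentence is ambiguous; it is not a proven removal rule.

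**A reader might also express the shift as a share of a 0.5 SD effect.** The only stated effect size is f = 0.25, for a repeated measures ANOVA (E.2), where the named analysis concerns feeding practices. No target difference or SD for the z score is given, so that benchmark would be the reader's own.

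**Conclusion.** The failure-to-thrive clause is wrong as written. It can act only after randomisation, and on an event close to the outcome. If the intervention affects growth, or removal differs by arm, it distorts the group difference and conceals the main conceivable harm. For mean z the distortion attenuates a true downward shift. With no effect on growth and equal removal, the bias is zero, so it would be too strong to say that the comparison is biased in any event.

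The size is illustrative only. One infant at z = -2.5 shifts an arm mean by 0.125 (n = 20) or 0.167 (n = 15) if the others average 0. Under the assumed normal z scores with SD 1 and a sharp cut-off, a true fall is understated by about 14% to 30%. Definition, rate, SD and cut-off are all assumptions, because the protocol supplies none of them.

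The opt-out sentence is a secondary point of clarity.

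**What to change.** 1. In F.2, limit the exclusions to conditions known at enrolment.
2. State that infants who develop failure-to-thrive after randomisation stay in chart follow-up and are analysed in their assigned group.
3. Report failure-to-thrive by arm, with the definition used.
4. In E.1, replace the opt-out sentence with one saying that STOP ends the messages only, and that chart, visit-survey and recall data continue unless consent is withdrawn. Say also whether the texted survey link and the reminder continue.

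None of this settles how affected infants are cared for or whether their messages change.

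The cost is a few sentences in an amendment and, if needed, matching wording in the consent form. Weights and lengths already come from chart review, so no new measurements are needed. The downside is slight dilution of the estimated effect from opt-outs kept in the analysis.
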